## **IV. HUMAN SUBJECTS**

The proposed study will take place at UCLA and Mayo Clinic. In accordance with NIH policy, both sites have implemented mandatory educational programs for all study personnel on the protection of subjects in human research. Procedures are in place at both institutions to track the compliance of investigators with these programs. All key personnel will maintain current training certificates throughout the duration of this study. Certificates of training completion will be kept on file at both sites.

The study protocol will be submitted to the Institutional Review Boards (IRB) at each site for full review. This study is a randomized clinical trial that meets the federal definition of moderate risk. Subject enrollment will not begin until IRB approval is obtained. Written consent will be obtained from all subjects using IRB approved consent forms. All patient recruitment materials and announcements will be approved by the IRBs.

### **A. Involvement of human subjects**

**1. Number of subjects** - We plan to recruit 240 subjects during the 5-year grant period, equally divided between the two study sites.

**2. Inclusion/exclusion criteria.**

Patients who meet all inclusion and exclusion criteria listed in the "Study Plan" and agree to take part in the study will be enrolled after providing written informed consent. Adults >65 years of age will be excluded from the study because FDA registration trials for rizatriptan did not include adults in this age group. Children <18 years of age will be excluded because the safety and efficacy of rizatriptan for VM has not been established and VM is a condition affecting adults more than children. Subjects must be mentally and physically capable of participating in all aspects of the study. Based on our prior experience and the known demographics of vestibular migraine (VM), we expect to enroll more women than men. The majority of subjects will be non-Hispanic white, but we will actively recruit patients from diverse racial/ethnic backgrounds.

Determination of eligibility. The PIs and Co-investigators will make final determinations of potential subject eligibility after reviewing clinical history, physical examination and test results, and final clinical diagnoses.

Special inclusion or exclusion criteria. None.

**3. Vulnerable subjects.**

We will exclude children (<18 years of age) from this study. We also will exclude older adults (>65 years of age) from this study (See IV.A.2). No members of other vulnerable groups will be targeted for recruitment.

### **B. Procedures**

Study procedures are summarized Table 2 of the study protocol. The study involves three visits to the study sites, an Observation Phase and a Treatment Phase. At the Enrollment Visit, investigators will verify eligibility, obtain written informed consent, and gather initial data. Subjects will complete the self-report measures listed in Table 2. This visit is expected to last 2-3 hours. After the Enrollment Visit, subjects will enter up to a 12 month Observation Phase during which they will record descriptive data and ratings for each vertigo attack that they suffer, along with associated symptoms and treatments. The research coordinator will contact subjects on a monthly basis to review these data. Phone interviews are expected to last less than 30 minutes. During the Observation Phase, investigators will prospectively evaluate patients for comorbid medical and psychiatric conditions. Investigators will treat these conditions themselves or enlist the care of relevant medical specialists as indicated. Subjects may return to the study centers for ad hoc visits, if needed for additional evaluations. Subjects will continue in the observation period until they have two vestibular attacks that meet the inclusion criteria or until the 12 months are up.

Once they have experienced two qualifying vestibular attacks or at the end of the Observation Phase, subjects will return to their study center for a second visit. Investigators will collect interval history and subjects will complete the self-report measures listed in Table 2. This visit is expected to last 2 hours. Subjects who experience at least two vestibular attacks of moderate or greater severity during the Observation Phase and demonstrate acceptable adherence with data gathering and reporting procedures will be randomized to treat three subsequent vestibular attacks with either rizatriptan or placebo (ratio 2:1) in randomized and double-blind fashion. Subjects will rate treatment response and adverse effects. They will contact study personnel to review these data at 48 hours after each vestibular attack treated with study medications. The research coordinator will contact subjects on a monthly basis by phone to review progress, assess adherence, and gather data on any interval change that might affect treatment response or safety. The Treatment Phase may last as short as 6 days for subjects who have three vertigo attacks in quick succession after randomization to as long as 4 years for subjects who enroll at the start of the study and do not have 3 treatable attacks before the end of the study. Subjects will return to the study site for an End Point Visit (visit 3) as soon as possible after treating three attacks or sooner if they will be withdrawn from the study for any reason. The End Point Visit is expected to last 2 hours.

### **C. Recruitment and consent**

Patients diagnosed with VM after completing clinical evaluations for episodic vertigo at UCLA or Mayo Clinic will be invited to participate in the study. Investigators will recruit patients that they see personally in their practices and patients seen by clinical colleagues at the study sites. Investigators will explain the study to potential subjects, answer questions, and provide subjects ample opportunity to read an IRB-approved written consent form describing the study. Subject who consent will be enrolled and begin study procedures. No study procedures will be performed before written informed consent is obtained. Potential subjects who decline to participate will be offered routine clinical care.

### **D. Potential Risks**

**1. Adverse Effects of Medication:** The primary risk to subjects will be the potential for adverse effects of study medication. There is a wealth of data documenting the safety and efficacy of rizatriptan in treating patients with migraine. In this randomized trial, we will use a dose of rizatriptan that is generally well tolerated by patients with migraine (10 mg). Common adverse events include: drowsiness (4-10%), dizziness (4-10%), nausea (4-8%), fatigue (1-7%), tingling or numb feeling (4%), dry mouth (3%), muscle pain or cramps (2%), and tightness in the neck or jaw (2%), tremors, chills, and flushing (feeling of warmth). Serious adverse events include chest pain (3%), hypertension, coronary artery spasm, myocardial infarction, peripheral ischemia, ventricular arrhythmia, ischemic colitis, anaphylaxis, angioedema, analgesic overuse headache, cerebrovascular accident, and serotonin syndrome.

**2. Loss of Confidentiality:** There is also a risk of loss of confidentiality if identifying information and data from medical records or study forms are inadvertently released.

**3. Time Demands:** This study places demands on subjects' time for completion of the Vertigo Symptom Diary and self-report instruments as well as monthly telephone appointments with investigators or research coordinators. The Vertigo Symptom Diary will have to be completed during and after each attack. Subjects will

track vertigo, headache, and associated symptoms in their diaries. They will rate each symptom using a single number from 0-3 at 0.5, 1, 2, 4, 12, 24, and 48 hours after the onset of each vertigo attack, which is expected to take 10-20 seconds at each time point or less than 3 minutes total per attack. Over the course of the study, subjects also will be required to complete 20 rating scales ranging in length from 7 to 36 questions. Each of these will take 1-5 minutes to complete for a total of about 80 minutes over the entire study. Telephone appointments are expected to be less than 30 minutes long on a monthly basis. During study Visit 1 only, subjects will complete a personality questionnaire that will take 30-40 minutes.

**4. Special circumstances involving studies assessing depression:** This investigation is not designed specifically to treat depression, but depression is more common in patients with vestibular disorders than in the general population. For that reason, all patients at Mayo Clinic in Rochester are screened for depression as part of clinical testing in the Vestibular Laboratory. Those who screen positive are examined by a Mayo Clinic psychiatrist or psychologist familiar with mood symptoms in patients with vestibular disorders. This has been part of routine clinical practice for 6 years. The presence of depression, per se, will not disqualify potential participants from study entry. Only those whose depression is judged unlikely to be brought under control within 3 months of study entry (e.g., treatment resistant depression, depression with suicidality or psychosis) will be ineligible to enroll. For others, treatment of depression will be part of the overall plan to manage common VM comorbidities during the Observation Phase, as described above (Section III.D.2).

Depression may affect the clinical course and treatment of VM. Therefore, depressive symptoms will be measured in all subjects at Visits 1, 2, and 3 using the PHQ-9 to gather data to control for this confound. Any subject whose PHQ-9 scores suggest clinically significant depression (PHQ-9 >9) or suicidal thoughts (PHQ-9 question 9 >0) will be examined by a study physician at the time of the visit to ensure that treatment for depression is initiated or updated and that the level of depressive symptoms is compatible with continued study participation. Patients judged ineligible will be disenrolled and provided or referred for appropriate treatment.

#### **E. Risk Minimization**

**1. Adverse Effects of Medication:** Subjects with ischemic heart disease, uncontrolled hypertension, or coronary artery vasospasm will be excluded from the study because of the known cardiac complications of triptans. Those who are allergic or unable to tolerate triptans in the past will also be excluded from the study. (See “Exclusion Criteria”).

Subjects will be closely monitored. The research coordinator will inquire about adverse events and changes in health status during monthly telephone interviews. Subjects will be instructed to contact a member of the research staff regarding adverse events at any time during the study. They will be instructed to report cardiac symptoms or allergic reactions immediately. Subjects who develop treatment-related serious adverse events or new onset exclusionary medical conditions will be withdrawn immediately from the study.

**2. Loss of Confidentiality:** Confidentiality will be maintained to the extent legally permissible by the appropriate handling of patient records and study data. Data obtained from source documents, interviews and questionnaires will be captured on research forms, entered online, and stored at DSCC. The information will be kept confidential in a secure electronic database with restricted and monitored access. A unique subject ID number will be used for each subject’s research case report forms and all communications, in accordance with the Health Insurance Portability and Accountability Act. No identifying information will be entered into the database.

**3. Time Demands:** The Clinical Trials Subcommittee of the International Headache Society published guidelines for data collection during clinical trials of migraine treatments. The data collection instruments selected for this proposed study – a symptom diary and validated measures of functional impairment and quality of life – follow those recommendations. The specific diary method for rating symptoms during and after attacks was adopted from two major registration trials for rizatriptan, which included several hundred subjects each. The self-reports of dizziness handicap, quality of life, depression and anxiety have been used by thousands of patients in clinical and research settings around the world for many years. Specific scales were chosen to achieve the goals of the study, while keeping demands on subjects’ time to a minimum.

**F. Risk/Benefit Analysis:** A potential benefit to subjects who participate in this study will be the possibility of a

reduction in vestibular attack duration and/or severity and interference with daily activities as well as possibly improved quality of life. It is also possible that there would be no benefit to the study participants. A benefit to society may be greater understanding of treatment options for vestibular attacks in patients with VM.

**G. Gender/minority recruitment:** Men and women of all racial and ethnic backgrounds will have an opportunity to participate in this study. White women have been heavily over-represented in large pre-registration and post-marketing trials of rizatriptan, with most studies including about 90% white patients and 90% women. Our published research in VM included a 2:1 female:male ratio, in keeping with the known sex distribution of VM. We anticipate a similar sex ratio for subjects in this study. We project that 20% of our sample will be from minority groups.

## V. STUDY OVERSIGHT

The PI and Co-PI will have primary responsibility for the conduct of this clinical trial. A Data Safety Monitoring Board (DSMB) with oversight responsibility will be appointed by NIDCD. The DSMB will review subject accrual, frequencies and patterns of all adverse events, and protocol compliance on a quarterly basis and will make recommendations to the NIH regarding the continuation status of the protocol. Co-Investigator [name] will compile clinical data to prepare the reports for DSMB reviews.

The Principal Investigator, Co-PI and their research teams (co-investigators, research nurses, research coordinators, and others) will be responsible for identifying adverse events. Aggregate reports detailed by severity, attribution (expected or unexpected), and relationship to the study drug/study procedures will be made available by the DSCC for site review. A separate report detailing protocol compliance will also be available from the DSCC for site review monthly. The research team will review these reports monthly and determine whether the protocol or informed consent document requires revision based on the reports.

### A. Definitions/Standards

An adverse event is defined as an unfavorable and unintended sign, symptom or disease associated with a participant's participation in the current study.

Serious adverse events include those events that result in death, are life-threatening, require inpatient hospitalization or prolongation of existing hospitalization, create persistent or significant disability/incapacity, or cause a congenital anomaly or birth defects.

An unexpected adverse event is defined as any adverse experience, the specificity or severity of which is not consistent with the risks or information described in the protocol. Expected adverse events are those that are identified in the research protocol as having been previously associated with or having the potential to arise as a consequence of participation in the study.

All reported adverse events will be classified using the Common Terminology Criteria for Adverse Events (CTCAE), version 4, developed and maintained by CTEP at National Cancer Institute.

### B. Study Intervention and Procedures: Definition of Expected Adverse Events

Treatment Study Drug – Rizatriptan (10mg within a 48-hour period). Common adverse events include drowsiness (4-10%), dizziness (4-10%), nausea (4-8%), fatigue (1-7%), tingling or numb feeling (4%), dry mouth (3%), muscle pain or cramps (2%), tightness in the neck or jaw (2%), tremors, chills, and flushing (feeling of warmth). Allergic reactions include rash or redness, swelling, or itching of the eyelids, face, or lips. Serious adverse events include chest pain (3%), hypertension, coronary artery spasm, myocardial infarction, peripheral ischemia, ventricular arrhythmia, ischemic colitis, anaphylaxis, angioedema, analgesic overuse headache, cerebrovascular accident, and serotonin syndrome.

### C. Reporting Timeline

Local institutional reporting requirements to IRBs and DSMB remain the responsibility of the treating physician

and the PI and Co-PI.

1. Investigators must report any Serious Adverse Event (SAE) that is considered life-threatening/disabling or results in death of subject or is unexpected or unanticipated, within **24 hours** of learning of an event.
2. Investigators must report all other SAEs within **5 working days** of learning of the event.
3. Investigators must report all other suspected AEs within **20 working days** of the notification of the event or of becoming aware of the event.
4. All serious adverse events (SAEs) must be reported to the FDA.
  - a) Fatal or life-threatening AEs, regardless of causal relationship to study medication, must be reported to FDA on a MedWatch Form within 7 days of the event.
  - b) Serious, but not fatal or life threatening events, which are related and unexpected, must be reported to FDA on a MedWatch Form within 15 days of the event.
  - c) Other suspected AEs will be reported to FDA every quarter after the start of the study.

#### **D. Adverse Event Data Management System (AEDAMS)**

Upon entry of a serious or unexpected adverse event, the DSCC created Adverse Event Data Management System (AEDAMS) will immediately notify the PI and Co-PI and any additional agencies of any reported adverse events per study protocol.

Serious adverse events: Causality (definitely not related, probably not related, possibly related, probably related, definitely related) of the adverse event will be determined by a thorough review. A determination of the causal relationship of all AEs will be made based upon the package insert (Sections 6.1 and 6.2). The Adverse Event Data Management System (AEDAMS) maintains audit trails and stores data (and data updated) and communication related to any adverse event in the study.

Non-serious expected adverse events: Except those listed above as immediately reportable, non-serious expected adverse events that are reported to or observed by the investigator or a member of his research team will be submitted to the DSCC in a timely fashion (within 20 working days). Local site investigators are also required to fulfill all reporting requirements of their local institutions.

#### **E. Study Discontinuation**

NIH and local IRBs have the authority to stop or suspend this trial at any time. This study may be suspended or closed if:

- Accrual has been met
- The study objectives have been met
- The PI or Co-PI believe it is not safe for the study to continue
- The DSMB recommends to the NIDCD and it suspends or closes the trial
- The FDA suspends or closes the trial

#### **F. Subject Discontinuation**

An intent to treat approach will be used. All data acquired prior to termination for the reasons outlined below will be included in the primary analysis unless the subject withdraws consent. Every effort will be made to conduct a final study visit with subject upon withdrawal and subjects will be followed clinically until, if applicable, all adverse events resolve. The following events will result in subject discontinuation:

- Withdrawal of consent
- Withdrawal by the participant
- Withdrawal by the investigator  Intercurrent illness or event that precludes further visits to the study site or ability to evaluate disease

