## **J. Statistical Methods**

**1. Power Analysis.** The primary goal of this Phase II study is to demonstrate sufficient superiority of rizatriptan over placebo in the main outcome measure, 1a(1), to warrant a future Phase III trial. In the previous triptan study for VM (see Prior Controlled Study of Triptans for VM), the response rate for active drug was 3/8 (38%) versus 2/9 (22%) for placebo. If the small sample from that failed trial reflected a true response, then the odds ratio favoring the triptan for VM would be 2.1. To improve our estimate, we examined the results of two large registration trials that used a simple randomization design similar to the present proposal to test rizatriptan for conventional migraine. Those studies had response rates of 74% and 77% for rizatriptan versus 28% and 37% for placebo giving odds ratios of 7.4 and 5.7 favoring rizatriptan. The lower response rates in the VM trial most likely reflected the inadequate sample size, but could suggest that triptans are less effective for VM than conventional migraine. To account for this possibility, we took the limited results of Neuhauser, et al. as a worst-case scenario for our sample size calculation. Focusing on the main outcome measure, 1a(1), in this double-blind, randomized trial, with PASS simple randomization design and using a type I error of 0.05, type II error of 0.2 (equivalent to power of 80%), two-sided tests, then treating 120 subjects (with 2:1 ratio for treatment and placebo) will allow us to detect an odds ratio as small as 3.2. Thus, the plan to enroll 200 subjects in the Observation Phase and select 120 for the Treatment Phase will be sufficient, even if the response of VM to rizatriptan proves to be only half that of conventional migraine. Phase II trials typically gather data on secondary outcomes (e.g., 1a(2)-1d(2)) and other variables (2a-c) to inform the design of Phase III trials, but sample sizes need not be planned to demonstrate significant differences in these variables.

**2. Randomization.** A randomization scheme will be developed to assign the 120 patients expected to be included in the Treatment Phase to parallel treatment arms in a 2:1 ratio of active drug:placebo.

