4. We will use this 3-step analysis procedure to test all outcome measures for hypotheses 1a-1d. However, the principal result of the study will be determined by the findings of bivariate analyses and multivariate modeling of the main outcome measure, 1.a.(1), plus favorable findings on tolerability measures, 1d(1)-1d(2). We will include all subjects who treat at least one vertigo attack with study drug (i.e., intent-to-treat analysis). A statistically significant result favoring rizatriptan over placebo on 1a(1) and absence of statistically significant differences on 1d(1)-1d(2) will support development of a Phase III clinical trial of rizatriptan for treating vestibular attacks in patients with VM. The design of future trials will also be informed by results of tests of secondary measures 1a(2)-1c(2). We did not hypothesize equal tolerability for rizatriptan and placebo, but rather an absence of significantly higher rates of serious adverse effects and drug-related treatment discontinuation, so our statistical analyses of measures 1d(1)-1d(2) will not include equivalence tests.

[figure not shown]

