6. Missing Data: We do not anticipate a major problem with missing data from subjects who complete this study. Furthermore, repeated measures mixed effects models allow unbalanced data (e.g., missing follow-up data). Nevertheless, we will use the following approach to missing data. We will calculate the frequency and pattern of missingness of each measure as missing completely at random (MCAR), missing at random (MAR) or missing not at random (MNAR). Based on the nature of missingness, we will determine which imputation approach would be appropriate. For complex situations, we will use EM algorithm, fully Bayesian, maximum likelihood procedures, and parametric multiple imputation (MI) methods, which are appropriate under general MAR conditions. ML and MI tend to yield similar results when implemented in comparable ways. Nonrandom dropout may be a problem because subjects having the most severe attacks may object to taking placebo pills or seek alternative treatment. Subject demographics and illness characteristics can be used to test the MAR assumption. To reduce the possible impact of non-random dropout or MNAR missingness, subject characteristics variables will be used in the missing data model with MI/ML, which can reduce estimation bias due to MNAR missingness, and partially restore lost power due to missingness. We will examine the distribution of the outcome of interest (treated attacks in which subjects experience a reduction in severity rating) and the auxiliary variable, and apply joint modeling and MI methods to utilize the auxiliary information (e.g., subject characteristics). We will apply MNAR methods (e.g., selection models, pattern mixture models, and shared parameter models) to perform sensitivity analysis to evaluate model robustness.

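### Section V.F drops already-recorded data from the primary analysis when a subject withdraws consent, in conflict with the intent-to-treat set defined in Section III.J.3

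*Combined protocol and SAP*

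**What the plan says.** Two places define who is in the primary analysis.

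- Section V.F, Subject Discontinuation, opens with "An intent to treat approach will be used". Its next sentence keeps data gathered before a subject's termination, with one exception: such data "will be included in the primary analysis unless the subject withdraws consent". The list of discontinuation events that follows has "Withdrawal of consent" and "Withdrawal by the participant" as separate items and does not define the difference.
- Section III.J.3, step 4, states the population for the outcome analyses: "We will include all subjects who treat at least one vertigo attack with study drug (i.e., intent-to-treat analysis"). It contains no exception for consent.

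Section III.J.3, step 6 (Missing Data), comments on why subjects might leave: "Nonrandom dropout may be a problem because subjects having the most severe attacks may object to taking placebo pills or seek alternative treatment". It plans likelihood and multiple-imputation methods, plus sensitivity analyses for data missing not at random.

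**The concern.** The exception removes observed outcomes, not unobserved ones. Each subject may treat up to three attacks (Section III.D.4) and is asked after each dose which treatment they think they received (Section III.E, item 3). There is thus room to treat an attack, get no relief, and leave. If some of those exits are recorded as withdrawal of consent, ratings already in the database disappear from the primary comparison for a reason that arose after randomization and may depend on the result.

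Three things are at stake.

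- **The dataset is not determined.** Two analysts following different sections would build different primary datasets.
- **A label decides.** Whether valid ratings count depends on which of two undefined exit categories is recorded.
- **The missing-data plan is weakened.** The mixed models and imputation methods rely on observed ratings to account for later dropout. Deleting those ratings discards the information that would explain the exit and creates missing data that need not exist.

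**Working it through.** **1. The sections side by side.** Take a subject who is randomized, treats one attack, records the one-hour rating, and then withdraws consent.

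| Source | In the primary analysis? |
|---|---|
| III.J.3, step 4 | Yes: one attack was treated with study drug |
| V.F, if recorded as withdrawal of consent | No |
| V.F, if recorded as withdrawal by the participant | Yes: earlier data are kept |

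**2. The plan's own figure.** Section III.J.1 gives 120 subjects at 2:1 and a detectable odds ratio of 3.2, "using a type I error of 0.05, type II error of 0.2 (equivalent to power of 80%), two-sided tests". It takes the earlier zolmitriptan trial, with placebo response 2/9, as its worst case.

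- Placebo rate p0 = 2/9 = 0.222, so the odds are 2/7 = 0.286.
- Rizatriptan odds = 3.2 × 0.286 = 0.914, so p1 = 0.914/1.914 = 0.478.
- Pooled rate = (40 × 0.222 + 80 × 0.478)/120 = 0.392.
- SE under no difference = √[0.392 × 0.608 × (1/40 + 1/80)] = 0.0946.
- SE under the alternative = √[0.222 × 0.778/40 + 0.478 × 0.522/80] = 0.0863.
- Power = Φ[(0.255 − 1.96 × 0.0946)/0.0863] = Φ(0.81) = 0.79.

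For 80% power the same method needs 123 subjects, and at 120 it detects an odds ratio of 3.24. The plan's figure reproduces closely.

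**3. Effect of the exclusion on the odds ratio.** Let a fraction w of an arm's attacks be dropped, all of them non-responses. The arm's odds change from p/(1 − p) to p/(1 − p − w). So:

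- loss on placebo multiplies the odds ratio by (1 − p0 − w)/(1 − p0);
- loss on rizatriptan multiplies it by (1 − p1)/(1 − p1 − w).

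The documents give no rate, so w = 5% and 10% are assumptions.

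| Loss | w = 5% | w = 10% |
|---|---|---|
| Placebo only | 3.2 × 0.728/0.778 = 2.99 | 3.2 × 0.678/0.778 = 2.79 |
| Both arms | 2.994 × 0.5224/0.4724 = 3.311 | 2.789 × 0.5224/0.4224 = 3.449 |

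In the placebo-only case the observed placebo rate becomes 0.222/0.95 = 23.4% or 0.222/0.90 = 24.7%. If there is no true effect and only rizatriptan non-responders are lost, the apparent odds ratio is 0.778/0.728 = 1.07 or 0.778/0.678 = 1.15. With 40 placebo subjects planned, 5% to 10% is two to four people.

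**4. Effect on power** (0.792 with nothing dropped, true odds ratio 3.2; w = 2% added as a lower value).

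| Loss | 2% | 5% | 10% |
|---|---|---|---|
| Both arms, unrelated to outcome | 0.783 | 0.770 | 0.745 |
| Placebo non-responders only | 0.769 | 0.731 | 0.660 |

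The power figures treat each subject as contributing one outcome and ignore correlation among a subject's attacks. They are illustrative only.

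**The case against.** The strongest reply is that the exception is narrow and probably benign. Only withdrawal of consent triggers it. A subject who simply stops, or whom the investigator removes, keeps their earlier data in the analysis. The authors may have meant only subjects who refuse use of data already collected, and step 6 already plans sensitivity analyses for nonrandom dropout. The narrowness limits the size of the problem. It does not settle the conflict: Section V.F neither states that intent nor defines the two exit categories. Nor does step 6 say that its analyses cover ratings that were recorded and then removed.

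A reader might infer three stronger points that the documents do not support.

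- **That the exclusion is known to be outcome-related and biased against rizatriptan.** Step 6 says only that nonrandom dropout may be a problem, and it speaks of dropout in general. The trial is double-blind, so subjects in either arm may believe that they have placebo. As the working shows, losing non-responses in both arms raises the odds ratio.
- **That tolerability would look better than it is.** The exception names only the primary analysis. Nothing says that adverse-event data are deleted, and V.F has subjects followed until adverse events resolve. Step 4 does make tolerability part of the principal result, so the handling should be stated, but a distortion is not shown.
- **That the results bear this out.** The results summary at the end of the document mentions only a symptom-severity restriction (245 of 308 treated attacks used). Placebo supplied 92 of the 245, or 38%, against one third of subjects by allocation. That gives no sign of depleted placebo attacks, though it does not settle the question.

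The consent pages are not in the file, so what subjects were told about data already collected cannot be judged.

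**Conclusion.** The point holds as a conflict over the primary analysis population. Section V.F contains an explicit post-randomization exclusion of recorded outcomes. It is at odds with the intent-to-treat claim in the sentence before it and with the population in III.J.3, step 4. The exclusion is potentially outcome-related; the documents do not show that it is so.

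Size and direction are unknown. If the true odds ratio is 3.2, placebo response is 2/9, and 5% to 10% of attacks are lost with every lost attack a non-response, the apparent odds ratio ranges from 2.79 (placebo only, 10%) to about 3.4 (both arms, 10%). If the loss is unrelated to outcome, the cost at 2% to 10% is about 1 to 5 percentage points of power. This is a modest defect that should be corrected because the remedy is cheap. It does not by itself undermine the trial.

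**What to change.** Reconcile Section V.F with Section III.J.3, step 4, along these lines:

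- Withdrawal of consent ends further data collection.
- Efficacy and safety data recorded before the withdrawal stay in the primary and safety analyses.
- The sole exception is a subject who also withdraws permission to use data already collected.
- Define withdrawal of consent and withdrawal by the participant so that the two can be told apart.
- Report any subjects and attacks excluded under the exception, by arm.
- State that the sensitivity analyses in step 6 cover those exclusions.

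Align the consent wording if it does not already say this. The cost is one replaced protocol sentence, short additions for the definitions and reporting, and possibly matching consent text. No new data are collected, and the planned 120 subjects and power of about 0.79 are unchanged.
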